### **4.3 Intervention**

Patients in this single-arm study will undergo near-total endoscopic resection of skull base tumors ( $\geq 80\%$ ) followed by concurrent cisplatin-based chemotherapy with proton-beam radiation.

#### **4.3.1 Descriptions of PRO Instruments**

The PRO instruments and outcomes chosen for the proposed trials are well justified, hypothesis-driven, validated, reliable and meaningful to patients. Each instrument is described below. We estimate that patient response burden to complete these instruments will be approximately 35 minutes. The PRO instruments will be administered to patients preoperatively, at timepoints during the radiation and chemotherapy treatment period, and at post-treatment follow-up visits.

#### **4.3.2 Standard of care PRO instruments currently implemented**

Current standard of care PRO instruments will be used to prospectively collect data from all head and neck surgery and radiation therapy patients on this trial. We will use the EORTC HN measure and SBI measure.

#### **4.3.3 Study Specific PRO Instruments**

##### **4.3.3.1 EORTC QLQ H&N 43 and C30**

The European Organization for Research and Treatment of Cancer Quality of Life Questionnaire Head and Neck Module 43 (Appendix 1) is a validated 43-item site-specific assessment tool. The module uses 12 multi-item scales to measure problems with swallowing, salivating, senses, speech, social eating, pain, anxiety, body image, teeth, skin, shoulder and physical contact. In addition, 7 single-item scales are utilized in assessing problems with mouth opening, coughing, , neurology, weight loss, lymphedema and/or a wound, and, finally, social contact. All questions are based on a 4-point scale ranging from "not at all" to "very much."

The scoring procedure for the QLQ-H&N43 transforms all of the scale and single-item scores to range from 0 to 100. All QLQ-H&N43 scores are symptom scores, with higher scores

representing higher levels of symptomatology/problems. Internal consistency reliability for the multi-item scales was generally acceptable (Cronbach's alpha  $\geq 0.70$ ) in the validation.

The EORTC QLQ H&N 43 module was designed to be used together with the core questionnaire QLQ C30 (Appendix 2), which is an assessment of general well being. The EORTC QLQ-C30 (Appendix 2) is a 30-item questionnaire designed to assess the quality of life of cancer patients. The 30 items of the QLQ-C30 yield both multi-item scale scores and single-item scores, for a total of 15 distinct scores. These include one Global Health Status/QoL scale (2 items), five functional scales (Physical Functioning, 5 items; Role Functioning, 2 items; Emotional Functioning, 4 items; Cognitive Functioning, 2 items; and Social Functioning, 2 items), three symptom scales (Fatigue, 3 items; Nausea and Vomiting, 2 items; and Pain, 2 items), and six single item symptom scores (Dyspnea, Insomnia, Appetite Loss, Constipation, Diarrhea, and Financial Difficulties; all from single items). The questionnaire asks patients to indicate the extent to which they have experienced each of the problems "during the past week" on a 4-point Likert-type scale from "Not at all" to "Very much". The 2 exceptions are the 2 items of the Global Health Status/QoL scale, which patients are asked to rate on a 7-point scale from "Very poor" to "Excellent". The scoring procedure for the QLQ-C30^42 transforms all of the scale and single-item scores to range from 0 to 100. High scores for the Global Health Status/QoL scale represents high QoL, high scores for the functional scales represent high/healthy levels of functioning, but high scores for the symptom scales/items represent high levels of symptomatology/problems. The instrument has been extensively validated and is widely used in clinical trials. The multi-item scales generally have good internal consistency reliability coefficients.

#### **4.3.3.2 Skull Base Inventory**

Skull Base Inventory (Appendix 3) is a 41-item site-specific assessment tool designed to assess quality of life in patients with anterior skull base pathology. The SBI covers 11 disease-specific domains, including emotional, social, physical, cognitive, family, financial, spiritual, endocrine, nasal, neurologic, and visual. The 41 items are based on a 7-point scale ranging from "severe problem" to "no problem". Each domain is scored out of 100 with lower scores associated with poorer quality of life. Items within each domain for which a response was recorded were summed and averaged out of 100. A composite score assuming equivalent weighting of domains in overall quality of life was created by averaging domain scores. Recently, the SBI has been validated and shown to be reliable in assessing disease-specific quality of life for patients undergoing both endoscopic and open skull base surgery.

## **5.0 THERAPEUTIC/DIAGNOSTIC AGENTS**

### **5.1 Endoscopic Resection**

As described previously, endoscopic resection follows the principles of open surgery, with emphasis on oncologic considerations. In brief, an endoscope is used and two surgeons perform the intervention in a binostril manner. Tumor is generally resected with an emphasis on identification of the attachments in the paranasal sinuses, nasal cavity, or skull base. In the region of attachment, negative margins are obtained by removing a tissue layer beyond the area where the tumor is present. If the tumor has invaded the skull base, the skull base is removed and, if necessary, dura is also removed. If the tumor has invaded the orbital wall, then the affected bone is removed and, if necessary, periorbital tissue is removed. Margins are obtained and mapping can be performed to assist in focusing the adjuvant radiation treatment. In cases in which one layer of tissue beyond the tumor is not resectable (e.g., if the extratumoral layer is the carotid artery, orbital apex, or other unresectable tissue), tumor is

removed only to that layer, if feasible. Use of recently integrated technology, mainly high definition straight and angled endoscopes, as well as intraoperative image guidance (CT/MRI/PET), have made this surgical technique significantly safer.

## **5.2 Adjuvant Proton Radiotherapy**

Proton therapy treatment will follow the National Cancer Institute's "Guidelines for the Use of Proton Radiation Therapy in NCI-Sponsored Cooperative Group Trials" (<https://rrp.cancer.gov/content/docs/proton.doc>). Proton therapy techniques may include passively scattered or scanning or pencil beam technology.

## **5.3 Cisplatin Chemotherapy**

Cisplatin should be administered on day 1 (+/- 3 days) of the start of radiotherapy and then every 3 weeks (unless there is a delay for safety concerns such as neutropenia) for a total of 3 cycles. Treatment can be given over 1 day or split over 2 days. The chemotherapy will be administered per MSKCC guidelines at 100 mg/m^2 (dose reductions after the first cycle allowed for toxicity). Normal scheduled treatment can be +/- 72 hours from three weeks post the prior administration. Administration entails fluid and anti-emetics as per institution standard. Cisplatin should be infused over one hour. Cisplatin can be administered before or after radiation is given but is only started once the radiation program has been initiated. If cisplatin treatment is contraindicated after the first cycle of treatment due to toxicity (e.g., kidney failure), a change in chemotherapy is allowed after a discussion with the medical oncology co-PI.

## **5.4 Cisplatin with etoposide chemotherapy**

If the final pathology shows SNUC, at the discretion of the treating medical oncologist, the patient will receive cisplatin on day 1(+/- 3 days) of the start of radiotherapy and then every 3 weeks (unless there is a delay for safety concerns) for a total of three cycles. In addition to cisplatin at 60 mg/m^2 on day 1, the patient will receive etoposide chemotherapy at a dose of 120 mg/m^2 on days 1-3. Normal scheduled treatment can be +/- 72 hours from three weeks post the prior administration. The chemotherapy will be administered per MSKCC guidelines (dose reductions after the first cycle allowed for toxicity). Administration entails fluid and anti-emetics as per institution standard. Cisplatin can be administered before or after radiation is given but is only started once the radiation program has been initiated. If cisplatin treatment is contraindicated after the first cycle of treatment due to toxicity (e.g., kidney failure), a change in chemotherapy is allowed after a discussion with the medical oncology co-PI.

# **6.1 CRITERIA FOR SUBJECT ELIGIBILITY**

## **6.2 Subject Inclusion Criteria**

- Age greater than or equal to 18 years.
- Histopathologically confirmed diagnosis of one the following cancer types:
  - Squamous cell carcinoma
  - Esthesioneuroblastoma
  - Adenoid cystic carcinoma
  - Adenocarcinoma

- Paranasal sinus/nasal cavity malignancy is considered unresectable with negative margins surgery or resection would be considered excessively morbid. This could include lesions with:
  - Carotid involvement
  - Cavernous sinus invasion
  - Brain invasion
  - Orbital apex
  - Intraconal space
  - Pterygoid musculature involvement
  - Invasion of the clivus
- Resection of at least 80% of the volume of the tumor is feasible. Resectability will be determined by the surgeon and radiologist after discussion among the multidisciplinary team. For patients who have had surgery at an outside institution, the same parameters will be thoroughly screened to ensure the patient met the same inclusion criteria and resection standards.
- Patients must be a candidate for surgery (as per treating surgeon) and be able to tolerate proton radiation and chemotherapy (as per treating radiation oncologist and medical oncologist).
- Karnofsky performance status  $\geq 70$ .
- The subject has organ and marrow function and laboratory values rendering safe administration of Cisplatin:
  - The ANC  $\geq 1000/\text{mm}^3$  without colony stimulating factor support;
  - Platelets  $\geq 100,000/\text{mm}^3$ ;
  - Hemoglobin  $\geq 9 \text{ g/dL}$ ;
  - Bilirubin  $\leq 1.5 \text{ } \square \text{ the ULN}$ . For subjects with known Gilbert's disease, bilirubin  $\leq 3.0 \text{ mg/dL}$ ;
  - Serum albumin  $\geq 2.8 \text{ g/dL}$ ;
  - Creatinine clearance (CrCl)  $\geq 60 \text{ mL/min}$ . For creatinine clearance estimation, the Cockcroft and Gault equation should be used:
    - Male: CrCl (mL/min) =  $(140 - \text{age}) \times \text{wt (kg)} / (\text{serum creatinine} \times 72)$ ;
    - Female: Multiply above result by 0.85;
  - ALT and AST  $\leq 3.0 \text{ } \square \text{ ULN}$ ;
  - Serum phosphorus, calcium, magnesium and potassium  $\geq \text{LLN}$ .
- No evidence of intercurrent infection.
- Negative pregnancy test for women of childbearing potential ( $<51$  years of age) as per institutional policy.
- Patient must be able to read and write in English.
- Patients who initially meet the histopathological inclusion criteria but surgical pathology report shows Sinonasal Undifferentiated Carcinoma.
- 

### 6.3 Subject Exclusion Criteria

- Tumor is deemed to be resectable with negative margins by conventional surgical standards.
- Patients not able to receive standard-dose cisplatin based on the judgement of the

treating medical oncologist.

- Patients with chronic kidney disease (GFR <60), uncontrolled hypertension, congestive heart failure, pre-existing bone marrow dysfunction, or cytopenias.
  - Congestive heart failure (CHF): New York Heart Association (NYHA) Class II-IV at the time of screening;
- Concurrent uncontrolled hypertension defined as sustained blood pressure (BP) > 150 mm Hg systolic or > 100 mm Hg diastolic despite optimal antihypertensive treatment within 7 days of the first dose of study treatment; If severe hearing impairment is measured or if significant neuropathy is reported at baseline the treating physician will discuss the risks for further permanent hearing loss and neuropathy with the patient.
- Patients not able to have a MRI (due to pacemaker, claustrophobia, etc.).
- Inability to return to MSKCC for frequent scheduled hydration sessions post-chemotherapy.
- Inability to comply with requirements for cisplatin administration anti-emetic regimens post-treatment.
- Patients not able or unwilling to travel for proton therapy.
- Patients with distant metastatic disease.
- Patients with prior radiation to the head and neck.

## 7.0 RECRUITMENT PLAN

### 7.1 General Recruitment Plan

Patients will be evaluated by an attending physician from the Department of Radiation Oncology, the Division of Head and Neck Surgery, Department of Surgery, the Department of Neurosurgery, or Department of Medical Oncology, and entered into the study if they are appropriate candidates. The attending physician will obtain informed consent from the eligible patients.

The protocol investigator, co-investigator(s), or a member of the treatment team can screen medical records of patients with whom they have a therapeutic relationship to identify potential research subjects eligible for this study. In addition, protocol investigator, co-investigator(s), and research study assistant(s) can screen medical records of patients with whom they do not have a therapeutic relationship for the limited purpose of identifying patients who would be eligible to enroll in the study, and to record appropriate contact information in order to approach these patients regarding the possibility of enrolling in the study.

During the initial conversation between the investigator, the research staff, and the patient, the patient may be asked to provide certain health information that is necessary for the recruitment and enrollment process. The investigator/research staff may also review portions of the patient's medical records at MSKCC in order to further assess eligibility. They will use the information provided by the patient and/or medical record to confirm whether the patient is eligible and to contact the patient regarding study enrollment. If the patient is deemed ineligible for the research study, the investigator and/or research study assistant will destroy all information collected during the initial conversation and medical records review, except for any information that must be maintained for screening log purposes.

In most cases, the initial contact with the prospective subject will be conducted either by the treatment team, the investigator, or the research staff working in consultation with the treatment team. The recruitment process outlined presents no more than minimal risk to the privacy of the patients who are screened, and minimal PHI will be maintained as part of a screening log. For these reasons, we seek a (partial) limited waiver of authorization for the purposes of (1) reviewing medical records to identify potential research subjects, and obtain information relevant to the enrollment process; (2) conversing with patients regarding possible enrollment; (3) handling of PHI contained within those records and provided by the potential subjects; and (4) maintaining information in a screening log of patients approached (if applicable).

After initial contact with the patient, our research team will contact the PROCure or New York Proton Center (NYPC) team to initiate financial approval. The financial team at ProCure or NYPC will work closely with the patient and their insurance plan to determine his/her financial responsibility in regards to proton therapy. The patient will have all appropriate information prior to enrolling on the protocol.

## 7.2 Gender/race breakdowns

In selecting patients for this study and the projects proposed in this protocol, we have taken due notice of NIH/ADAMHA policies concerning inclusion of women and minorities in clinical research populations. We expect that the study population will be representative of the range of paranasal sinus/nasal cavity patients seen at MSKCC. No specific outreach efforts are planned.

## 7.3 Target/planned enrollment

The anticipated accrual rate is 1-2 patients per month to meet the accrual goal of 25 patients (15 SCC and 10 ACC, esthesio, or Adenocarcinoma). Based on recent patient treatment patterns in the head and neck and radiation oncology services, we estimate that MSK treats approximately 20 patients each year who would be eligible for this trial. We do not anticipate any difficulties in meeting our accrual goal.

## 8.0 PRETREATMENT EVALUATION

All patients will receive the necessary scans and tests according to the standard of care for their paranasal/nasal cavity malignancy.

Table 2 contains all the tests that will be performed within 8 weeks of the start of surgery and then chemoradiation.

**Table 2: PRE-TREATMENT ASSESSMENTS**

[figure not shown]
Assessments	Source	Prior to protocol calendar days
Consent form signed by patient	CRC	1-3 weeks A
History B	EMR	30 days

Physical	EMR	30 days
Audiogram	EMR	6 weeks
CBC, CMP, Hepatitis B Core and Surface antigen	EMR	6 weeks
Dental Evaluation	EMR	6 weeks
Pregnancy test C	EMR	14 days prior to surgery
Karnofsky performance status	EMR	6 weeks
PET-CT with CT Neck component to include IV contrast and MRI of the Nasal Cavity/Para-Nasal Sinuses with contrast D	EMR	4 weeks
SBI	PSA	6 weeks
EORTC QLQ C30 & H&N 43	PSA	6 weeks

A: Patients start treatment within 30 days from time of consent as per institution's standard  
 B: For cisplatin eligibility requirement, a medical history for neuropathy, history of kidney disease, diabetes, hypertension, and cardiac disease.  
 C: For women of childbearing potential: Pregnancy testing should be performed according to institutional standards.  
 D: Patients with contrast allergies should be pre-medicated; patients with specific contrast contraindications can have contrast administration deferred.  
 Abbreviations: CRC (Clinical Research Coordinator);PSA (Patient self-administered with or without CRCAssistance); EMR (Electronic Medical Record)

## 9.1 TREATMENT/INTERVENTION PLAN

### 9.2 Therapy Schema:

## **9.1: Endoscopic Resection Treatment Technology**

Endoscopic skull base surgery will be performed as per standard of care for any patient with tumors of the paranasal sinus and skull base treated at MSK, as described above. For patients who have had surgery elsewhere, they will be enrolled as long as standard of care parameters per MSKCC were met at the outside institution. Tissue used for IMPACT testing will be taken from the main specimen during the operation. For those who have had surgery elsewhere, tissue will be requested from the outside institution. The corresponding blood required for IMPACT testing will be drawn prior to the surgery.

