## **4.1 OVERVIEW OF STUDY DESIGN/INTERVENTION**

### **4.2 Design**

This is a single center, phase II, single-arm trial assessing the efficacy of local control of near-total endoscopic resection followed by proton-beam radiation with concurrent chemotherapy in unresectable paranasal sinus/nasal cavity tumors. The primary endpoint is local control at 1 year from the end of treatment with failure defined as progression of disease by > 20% of the 12 month post treatment MRI (per RECIST) compared to the post- surgical MRI. If a patient dies during treatment, he/she will be counted as a failure. We will secondarily assess regional/nodal failure and distant metastases, overall survival, disease specific mortality, and progression free survival. Treatment toxicity will be assessed by the Clavien-Dindo Classification of Surgical Complications and CTCAE v4.03 as well as PRO measures including EORTC HN and SBI. IMPACT testing will be performed for all patients undergoing treatment for this rare disease. Results of IMPACT testing will be banked for future investigation. We will include patients with a variety of histologic diagnoses including squamous cell carcinoma (SCC), esthesioneuroblastoma, adenoid cystic carcinoma, and adenocarcinoma. Patients will be included if there is multidisciplinary consensus that the primary lesion is not resectable with negative margin surgery without significant morbidity. This could include lesions that (1) involve the carotid artery, (2) invade brain parenchyma, (3) involve the orbital apex, (4) invade the pterygoid musculature, (5) involve the cavernous

sinus, (6) involve the clivus, and/or (7) involve intraconal space. Patients will only be included if there is multidisciplinary consensus that at least 80% of the tumor bulk can be removed without significant risk of morbidity. There is no cut-off for residual disease. Although expected that we will resect >80% of patient's tumor as discussed pre-operatively, if less than this is resected, patient will still proceed with protocol. Patients will be stratified by the pathologic diagnosis.

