### **14.0 BIOSTATISTICS**

A one-stage design will be used for this trial. Of the 25 patients to be enrolled, 15 will be SCC patients and the remaining 10 will be ACC, Esthesio, or Adenocarcinoma. Based on historical data, current standard non-surgical treatment has a 1-year local failure rate of 40% for SCC patients and 65% for ACC, Esthesio or Adenocarcinoma patients. Therefore, a mixed cohort of 15 SCC and 10 ACC/Esthesio/Adenocarcinoma patients should have 1-year local failure rate of 50% under standard non-surgical treatment. We expect to decrease such a rate to 25% using the proposed new treatment. This design depends on a one-arm, one-sided binomial test and has a decision rule as follows: If, among the total 25 patients enrolled, we have at least 17 patients who are alive, followed and local failure free (or equivalently, at most 8 patients who are dead, lost to follow up or withdrew from the study, or have local failure) one year from the end of the treatment, then we shall declare the proposed treatment strategy

worthy of further investigation. Any patient who is taken off study due to unacceptable toxicities or lost to follow up, dies or withdraws within one year from the end of treatment will be regarded as a local failure. Patients who die during treatment will also be counted as failures, though such a probability will be small. This design has a type 1 error rate of 0.05 and type 2 error rate of 0.15 for testing the hypothesis  $p \geq 50\%$  vs  $p < 25\%$ , where  $p$  represents the 1-year local failure rate.

To assess the complications of minimally invasive endoscopic skull base surgery in patients with unresectable disease, we will use Clavien-Dindo classification of surgical complications and summarize the grades (I-V) and types. This will be done after surgery but before radiation.

To assess acute and long-term toxicity of radiotherapy, we will summarize the CTCAE v4.03 scores and present descriptive statistics. This will be done weekly throughout RT, at the end of RT, and then 3 months after the end of RT for acute toxicities. Long-term toxicities will be assessed at 6, 12 and 24 months after the end of RT.

Patient reported outcomes of toxicity due to radiotherapy, EORTC (H&N43 and QLQ C30) and SBI, will be summarized and reported at the following time points: After surgery (pre RT), week 4 of RT (+/- 7 days), 1 week within end of RT, and then at 3, 6, 12 and 24 months after the end of RT.

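### Patients operated on elsewhere enter only after coming through the experimental surgery, yet are pooled with patients counted from before it; this lowers the failure count and the surgical complication rate by an amount the documents cannot fix.

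*Combined protocol and SAP*

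**What the plan says.** Section 4.3 makes the resection the first component of the intervention, followed by cisplatin-based chemotherapy with protons. There are two ways in.

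**Surgery at the centre.** Section 4.2 selects patients on the expectation that at least 80% of the tumour can be removed, sets no cut-off for residual disease, and adds that "if less than this is resected, patient will still proceed with protocol". Section 13.1 does not replace patients who leave for unacceptable toxicity or are lost; they count as failures. Section 14.0 adds deaths and withdrawals within one year of the end of treatment, and deaths during treatment.

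**Surgery elsewhere.** Section 9.1 (Endoscopic Resection Treatment Technology) says: "For patients who have had surgery elsewhere, they will be enrolled as long as standard of care parameters per MSKCC were met". Section 6.2 says that for these patients "the same parameters will be thoroughly screened to ensure the patient met the same inclusion criteria and resection standards". The other entry criteria in Sections 6.2 and 6.3 also apply, including Karnofsky status of at least 70, ability to tolerate protons and chemotherapy, no intercurrent infection, no distant metastases, and ability to travel for proton therapy.

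**Analysis.** Section 14.0 uses one rule for everyone: "If, among the total 25 patients enrolled, we have at least 17 patients who are alive, followed and local failure free" one year after the end of treatment, the strategy is declared worth pursuing. Surgical complications are summarised by Clavien-Dindo grade after surgery and before radiation (Section 14.0; Table 3). Nothing caps, flags or separately analyses patients operated on elsewhere, or says how their complications before enrolment are ascertained.

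**The concern.** A postoperative death, or a complication that leaves the patient unfit for chemoradiation, is a counted event on one route and a patient who never appears on the other. This is selection at entry on the outcome of one component of the tested strategy.

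Two results are exposed. The primary failure count will be lower than if all 25 had been registered before surgery, other things being equal. Surgical complications, the first secondary objective listed, will look rarer than they are if outside patients are in the denominator, because those patients have been filtered on the worst grades. The trial's question is whether adding this surgery helps, so harm from the surgery belongs in both results.

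**Working it through.** **Inputs from Section 14.0.** The test: "This design depends on a one-arm, one-sided binomial test and has a decision rule as follows", with n = 25 and success at 17 or more failure-free, that is, at most 8 failures. The null: the mixed cohort "should have 1-year local failure rate of 50% under standard non-surgical treatment". The target failure rate is 25%. The stated error rates are 0.05 (type 1) and 0.15 (type 2).

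**Reproducing the plan's figures.** Standard treatment "has a 1-year local failure rate of 40% for SCC patients and 65% for ACC, Esthesio or Adenocarcinoma patients", and of the 25, "15 will be SCC patients and the remaining 10 will be ACC, Esthesio, or Adenocarcinoma".
- Pooled null: (15 × 0.40 + 10 × 0.65)/25 = 12.5/25 = 0.50.
- Type 1 error: P(X ≤ 8), X ~ Bin(25, 0.50), = 0.0539, printed as 0.05. With 15 patients at 0.40 and 10 at 0.65 it is 0.0483.
- Power: P(X ≤ 8), X ~ Bin(25, 0.25), = 0.8506, so type 2 error is 0.149. This agrees with the plan.

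**Assumptions, not in the documents.** Let k be the number of outside patients among the 25 (5 or 10 here). Let q be the share of operated patients who fail before chemoradiation and so would never be registered by the outside route (2% to 10% here). The documents do not say how q relates to the 50% null, so both readings are needed.

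- *Inside.* The 50% already contains the operative failures. Centre patients fail at 0.50 and outside patients at (0.50 − q)/(1 − q). For q = 0.10: 0.40/0.90 = 0.444.
- *On top.* The 50% applies to patients who reach chemoradiation. Outside patients fail at 0.50 and centre patients at q + (1 − q) × 0.50. For q = 0.10: 0.10 + 0.45 = 0.55.

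P(X ≤ 8) is then exact, from the convolution of Bin(25 − k, centre rate) and Bin(k, outside rate):

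| k | q | Inside | On top |
|---|---|---|---|
| 0 | 2% | 0.0539 | 0.0438 |
| 5 | 2% | 0.0561 | 0.0456 |
| 10 | 2% | 0.0585 | 0.0476 |
| 0 | 10% | 0.0539 | 0.0174 |
| 5 | 10% | 0.0670 | 0.0221 |
| 10 | 10% | 0.0825 | 0.0279 |

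**Direction.** Expected failures under the null at q = 10%:
- Inside: 12.5 for k = 0; 20 × 0.50 + 5 × 0.444 = 12.2 for k = 5; 15 × 0.50 + 10 × 0.444 = 11.9 for k = 10.
- On top: 25 × 0.55 = 13.75; 20 × 0.55 + 5 × 0.50 = 13.5; 15 × 0.55 + 10 × 0.50 = 13.25.

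On both readings pooling lowers the count relative to k = 0. Only the inside reading takes the type 1 error above the design's 0.0539.

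**Complications.** Let m be the true probability of postoperative death (Clavien-Dindo grade V). Outside patients contribute none, so with all 25 in the denominator the expected reported rate is m × (25 − k)/25: 0.8m for k = 5 and 0.6m for k = 10. Complications that leave the patient unfit for entry are filtered in the same way. Complications from which the patient recovered are not.

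**The case against.** The strongest objection concerns the type 1 error. The 50% comes from non-surgical treatment, which has no operative phase. Outside patients, entering at the start of chemoradiation, may therefore be the ones who match the historical controls, while centre patients carry an extra operative risk. On that reading the rule stays below its nominal size. This stands, and it is why a claim of inflated type 1 error, which a reader might infer, is not supported. It does not remove the difference from a cohort counted from before surgery.

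A large effect is not documented either. Section 14.0 calls death during treatment unlikely, Section 9.2.6 expects nearly all patients to complete therapy, and Section 11.1.1 gives low complication rates for endoscopic surgery. The 5% mortality in the background section is for open surgery. Section 7.3 expects about 20 eligible patients a year at the centre, so many outside patients may not be needed. Harder referrals could also offset part of the bias; the documents do not address this.

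Three further readings go too far:
- *Outside patients with less than 80% removed are refused, while centre patients stay.* The Section 6.2 sentence belongs to a criterion about feasibility, and the standards it names may concern feasibility or how the surgery was done. What remains is survival and fitness at entry.
- *Centre patients count whatever happens.* Section 13.1 leaves a patient later found ineligible to the treating physician's discretion.
- *Immortal-time bias.* The primary endpoint, progression and survival run from the end of treatment (Sections 12.1, 12.4, 12.6), so no event-free time before registration is credited.

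Finally, the Clavien-Dindo summary is descriptive, and no passage expressly puts outside patients in its denominator. But none takes them out, so the plan should say.

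**Conclusion.** The asymmetry is in the text and should be handled in the analysis. The direction is clear if the two groups are otherwise alike: pooling lowers the failure count and, if all 25 form the denominator, understates the surgical complication rate.

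The size cannot be fixed from the documents. For 5 to 10 outside patients and 2% to 10% early failure, the type 1 error is about 0.056 to 0.083 with operative failures inside the 50% null and about 0.022 to 0.048 with them on top, against 0.054 for the rule as designed. Both k and q are assumptions. Inflated type 1 error is possible but not established. The case for acting rests on interpretability and low cost, not on a demonstrated failure of the design.

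**What to change.** Keep enrolling these patients and keep the 25-patient decision rule. Add to Section 14.0:

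1. Record for each patient whether registration was before or after surgery.
2. Next to the pooled result, report the primary failure count with an exact confidence interval for patients registered before surgery, as a descriptive sensitivity analysis.
3. Base the Clavien-Dindo rates on patients registered before surgery, and list outside patients' complications separately.

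Do not make the pre-surgery subset a second go/no-go condition. As an illustration, also requiring at most 6 failures in a subset of 20 would cut power from 0.85 to about 0.76; at most 4 in a subset of 15 would cut it to about 0.66 (both at a 25% failure rate for all patients).

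The cost is one case report form field and one table, with no change to accrual, treatment or the primary test. The downside is a smaller n for the surgical complication rates: 20 or 15 instead of 25 if 5 or 10 patients come from outside.
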